#### 6.4.5 Randomisation and Blinding Processes

##### Randomization

There is no randomization in this study.

##### Blinding

Blinding of the treating clinicians or the participants is not possible as this is a behavioural RCT. The treating clinicians are not able to deliver the intervention without knowing about it. The participants will not be blinded to the study treatment as they will know from recruitment that the treatment aims to improve speech. The clinicians scoring the assessments and transcribing the data will be blinded to pre-treatment performance and sequence of recordings.

## 6.5 Primary and Secondary Outcome Measures

### The primary outcome measure:

Speech intelligibility. This refers to how easy it is to understand the person's speech. This is measured with: *Assessment of Intelligibility in Dysarthric Speech* Standard Score

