**2. SYNOPSIS**

TITLE	Rapid Syllable Transition Treatment for Adults
PRIMARY HYPOTHESIS	That Rapid Syllable Transition Treatment (ReST) will be effective in improving speech intelligibility of adults with apraxia.
DESIGN	Single case experimental design – multiple baselines within participants
BLINDING/MASKING	Single blind As a behavioural intervention trial, the treating clinicians and participants cannot be blinded to allocated group or intervention.
OUTCOMES	The primary outcome Speech intelligibility in single words Secondary outcomes 
 
1. Participant satisfaction with the intervention
 
2. Speech accuracy
 
3. Sentence complexity and length in speech
 

STUDY DURATION	Estimated study duration from initial enrolment until completion of data analyses is 21 months
INTERVENTION/S	Rapid Syllable Transition Treatment (ReST)
NUMBER OF PARTICIPANTS	6 in 1 group
POPULATION	Sample Size : n=6 Gender : Male and female Age : Adults aged over 18 Demographic group : N/A Diagnosis : Apraxia of speech from any cause
SELECTION AND ENROLMENT	Inclusion criteria: 
 
1) Aged over 18 years
 
2) Diagnosis of apraxia
 
3) No diagnosis of intellectual disability, dementia or other significant disorder which effects speech production.
 
4) Normal or adjusted-to-normal hearing (screened) and vision (self-report).
 

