#### Hypothesis:

1. ReST will be effective in improving speech intelligibility in adults

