**PROCEDURES**

1. Following consent, participants will be assessed by a qualified speech pathologist (one of the investigators) using standard speech pathology tools. This assessment will take no more than one hour. Tasks will include saying words and sentences, reading a passage, having a hearing screening and completing an oral movement assessment (OMA) which includes tasks such as stick out your tongue; lick your lips, alternate between a kiss and a smile and say /a/ for as long as you can (forms attached). The assessment will be audio and video recorded.
2. Following standard ReST protocol, one of the investigators will then create a list of words for each participant consisting of 20 treatment words, 10 control (untreated) words, 10 untreated generalisation sentences and 30 generalisation words. This list of 70 items is called the Probe list and participants will be asked to say it on a number of occasions described below.

3. Prior to treatment, each participant will be asked to say the 70 item probe list on five separate days (max 30 minutes per session) and these will be recorded as the baseline performance.
4. Treatment will be provided by a trained speech pathology student for one hour twice per week for six weeks at a mutually convenient time. Treatment consists of learning to say the nonsense words. No home practice is required. Treatment may be face-to-face in the on-campus speech pathology clinic or it may be on Zoom. This choice will be up to participant preference.
5. Immediately prior to the fifth and ninth sessions, participants will be asked to say the 70 word probe list and this will be recorded. 20 minutes on each occasion.
6. Immediately following the final (twelfth) session, participants will be asked to say the 70 word probe list and this will be recorded. 20 minutes.
7. Participants will return to the clinic one day, one week, two weeks and four weeks after finishing treatment and say the 70 word probe list on each occasion. On the one week and two week post treatment occasions, they will be asked to say the list twice. Each visit will take approximately 30-40 minutes.
8. Four weeks after completion of the treatment, participants will also repeat several of the tasks completed in the initial assessment (step 1) and say the probe list for the final time (60 minutes total)
9. Following the four week appointment a short report on their individual performance in treatment will be sent to each participant for their own records.

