#### 6.4.4. Eligibility and pretreatment assessment

Following consent, participants will complete the following assessment tasks to (1) measure their performance prior to treatment (2) provide information for therapy planning (3) provide adequate description of each participant's communication skills and (4) to ensure they meet the inclusion and exclusion criteria. All tasks are standard speech pathology practice:

1. Complete a case history questionnaire
2. Hearing screening
3. Oral musculature evaluation – an examination of the structure and function of the muscles of speech
4. Apraxia Battery for Adults 2nd edition (speech and oral apraxia evaluation)
5. Apraxia Severity Rating Scale (speech tasks)
6. Assessment of Intelligibility in Dysarthric Speech (speech tasks)
7. PALPA – nonword repetition, sentence comprehension and reading letter names subtests
8. Picture description – the participant will be asked to verbally describe a picture.

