### **6.14 Statistical analyses**

Data analysis will utilize repeated measures visual analysis. When a treatment effect is evident visually, statistical analysis within participant, across treatment phase (I.e. baseline, treatment, follow-up) will be calculated using Helmert Planned orthogonal contrasts.

Effect sizes within participant will be calculated using  $d^2$ , as this measure is appropriate for single case data (Beeson & Robey, 2006).

If there is any attrition, an intention-to-treat analysis will be conducted.

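### The primary outcome is not on the repeated-measurement schedule that the only stated analysis needs, so the phase contrasts and within-participant effect size cannot be formed for it

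*Protocol*

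**What the plan says.** The protocol has one hypothesis (section 4): "ReST will be effective in improving speech intelligibility in adults". Section 6.5 ties the primary outcome to one instrument: "This is measured with: *Assessment of Intelligibility in Dysarthric Speech* Standard Score". The synopsis describes the same outcome as "Speech intelligibility in single words"; section 6.5 does not restrict it to single words.

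The instrument appears by name in one place in the schedule, as item 6 of the pre-treatment battery in 6.4.4. The only step that could bring it back is step 8 of the procedures in 6.2: "Four weeks after completion of the treatment, participants will also repeat several of the tasks completed in the initial assessment (step 1"). Neither step 8 nor step 1 names the intelligibility test.

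What is measured repeatedly is the probe list. Step 3 sets the baseline: "Prior to treatment, each participant will be asked to say the 70 item probe list on five separate days". Steps 5 to 8 then schedule it during and after treatment. Section 6.5 uses the probe data for percentage of phonemes correct, under the secondary outcome of speech accuracy.

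Section 6.14 gives one analysis for the study and names no outcome. It starts with visual analysis. If an effect is visible, "statistical analysis within participant, across treatment phase (I.e. baseline, treatment, follow-up) will be calculated using Helmert Planned orthogonal contrasts". A within-participant effect size follows. No pre/post or across-participant analysis is stated.

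**The concern.** A multiple-baseline single-case design draws its strength from several measurements in each phase. They show whether the baseline is stable, whether change begins with treatment, and how large the change is against ordinary variation. Here that repeated series exists for a secondary outcome, while the primary outcome stays outside it.

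This matters because intelligibility is the sole hypothesis, and section 3.2 expects the results to inform the sample size of a larger study. If 6.14 is applied to the primary outcome as written, its quantities do not exist. If step 8 is read narrowly, a site could omit the four-week intelligibility test without breaching the protocol, and a measurement not taken then cannot be recovered.

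**Working it through.** The protocol gives no alpha, power or assumed effect, so there is no stated figure to reproduce. The check counts scheduled measurements per participant and asks what 6.14 can estimate from them.

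**Counts** (6.4.4 item 6; 6.2 procedures, steps 3 and 5 to 8)

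| Phase | Intelligibility test | Probe list |
|---|---|---|
| Baseline | 1 | 5 |
| Treatment | 0 | 2 (before sessions 5 and 9) |
| After treatment | 0 or 1 | 1 + 1 + 2 + 2 + 1 = 7 |
| Total | at most 2 | 14 |

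The seven post-treatment probes are: straight after session 12 (1), one day (1), one week (2), two weeks (2) and four weeks (1). The four-week probe in steps 7 and 8 is counted once. Table 2 gives six visits (3 to 8) to pre-treatment probes where step 3 gives five days. The count of 14 follows the steps, and the conclusion does not depend on it.

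**Phase contrasts, intelligibility test, best case (1, 0, 1).** Write the phase means as (baseline, treatment, follow-up).
- The design rows are (1, 0, 0) and (0, 0, 1), so the rank is 2 for 3 phase means.
- Residual df = observations − rank = 2 − 2 = 0.
- Helmert contrasts in phase order are (1, −½, −½) and (0, 1, −1). Both use the treatment mean, which has no data, so neither is estimable.
- In the reverse direction, (−½, −½, 1) and (1, −1, 0) fail for the same reason.
- Only (1, 0, −1), the plain pre/post difference, is estimable. With 0 residual df it has no within-participant error term.

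**Worst case (1, 0, 0).** If the test is not among the repeated tasks, there is one observation and not even a difference.

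**Effect size.** The protocol does not write out the formula. I assume a standardised measure, scaled by some within-participant SD. The baseline SD has 1 − 1 = 0 df, and pooling within phases also gives 0 df. Either way it is undefined.

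**Visual analysis.** Two points can be plotted, one in each of two phases. Nothing within a phase can be judged.

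**The same analysis on the probe list (5, 2, 7).** Rank 3, residual df = 14 − 3 = 11, both Helmert contrasts estimable, baseline SD on 5 − 1 = 4 df. Counting the probe straight after session 12 as treatment gives 5, 3, 6 and the same 11 df. The stated analysis fits the probe outcome and does not fit the primary one.

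**The case against.** **Section 6.14 names no outcome.** Visual analysis of repeated measures most naturally describes the probe series. On that reading the protocol is silent on the primary outcome and does not prescribe an impossible analysis, and a statistical analysis plan could supply a paired comparison. This stands in part. But such a plan cannot create treatment-phase or repeated-baseline measurements that were never scheduled, nor make a four-week test mandatory when the protocol does not name it. The mismatch lies between 6.2, 6.4.4, 6.5 and 6.14 of the same document.

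**A four-week repeat is very likely intended.** The apraxia severity rating is also listed only in the initial battery, and the picture description used for utterance length first appears there. Both are secondary outcomes that lean on step 8, and utterance length is defined through change. Section 6.4.5 also blinds scorers to pre-treatment performance and to the order of recordings, which fits a repeated assessment. This stands. A reader might infer that the trial will have no post-treatment intelligibility score; the text does not support that. It supports only that the score is not guaranteed.

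**The study is small and early by design.** Section 6.3 calls it phase 1, meant to supply data for a later calculation, and up to six pre/post changes would give a mean and an SD for that. This also stands. Six participants is not the complaint, and the protocol sets no power standard against which to judge it.

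**Conclusion.** The point holds as a mismatch between measurement schedule and analysis. For the primary outcome there are at most 2 observations per participant, none during treatment and 0 residual df. The Helmert contrasts and the within-participant effect size cannot be estimated, and visual analysis has nothing to interpret within a phase. The probe list has 14 administrations and 11 residual df but serves a secondary outcome. The multiple-baseline design therefore does not support inference on the sole hypothesis.

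A reader might go further and conclude that the hypothesis must go untested. The documents do not support that: if the test is repeated at four weeks, a pre/post change can be computed for each participant and averaged. What is missing is a guaranteed second score and a stated analysis of it. Even then the change is uncontrolled. It has no counterpart to the untreated control words in the probe list, and it cannot separate treatment from retest effects or day-to-day variation.

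A reader might also infer that a probe measure should become primary, or that intelligibility should be rescored from probe recordings. Neither follows. The first detaches the primary outcome from the hypothesis. The second replaces the named Standard Score with a new measure taken largely from individually built pseudoword material.

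The verdict assumes that 6.4.4 and the steps in 6.2 are the full schedule, and that the effect size is scaled by a within-participant SD.

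**What to change.** 1. In step 8 of the procedures (6.2), name the Assessment of Intelligibility in Dysarthric Speech as a mandatory repeat at four weeks. State in both the synopsis and 6.5 whether the single-word score is the primary measure; the two places now differ in how specific they are.
2. In 6.14, state that the visual analysis, Helmert contrasts and within-participant effect size apply to the probe-based outcome.
3. In 6.14, state the analysis of the primary outcome: each participant's pre/post change, and the mean change across participants with a 95% CI (6 − 1 = 5 df if all six have both scores). Word the intelligibility conclusion as preliminary, giving the reason that the change is uncontrolled.

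Cost: a protocol amendment, which section 6.10 routes through the ethics committee and the registry, and a weaker claim about intelligibility. No extra participants or visits are needed, since the four-week visit already includes repeated assessment tasks.

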### The secondary outcome measures:

2: Satisfaction with the intervention .

- a. This is measured with a questionnaire containing Likert scales and open ended responses. The questionnaire will be provided to participants at the 1-week post treatment point and can be completed online at a time of their choosing.

3: Speech accuracy. This is measured with:

- a. **Percentage of phonemes correct in words.** The percentage of phonemes correct (PPC) expresses the percentage of consonant sounds that are articulated correctly. It is considered a robust means of assessing articulation accuracy (Shriberg et al., 1997) and will allow comparison with previous ReST research. It is calculated from the probe data
- b. **Apraxia of Speech Severity Rating scale** (Duffy et al., 2023 etc). This scale will allow us to compare this study with other Apraxia intervention studies.

4: Sentence complexity. - This is measured with:

- a. **Mean length of utterance (MLU) in speech.** Changes in the participant's mean length of utterance, as measured by calculating the average number of morphemes in a person's utterances (Miller & Chapman, 1981). This measure allows us to understand changes in everyday speech as a result of increasing speech success. It is calculated from a picture description or conversation.

## 6.6 Intervention

### 6.6.1 Rapid Syllable Transition Treatment (ReST; McCabe et al., 2017)

ReST involves the person saying multisyllabic pseudowords to improve the ability to transition rapidly and fluently from one sound/syllable to the next, and control of the melody in the form of relative emphasis, or stress, placed on each syllable within a word (McCabe et al., 2017).

Based on the baseline assessment, four vowels and four consonants are selected and used to form pseudowords, for example, consonants b, p, k, and m are combined with vowels to create pseudowords bamaka, makaba, mikabu and bamipa. The practise phase includes 100 attempts at producing the pseudowords. If the person is unable to complete saying all 100 pseudowords within the session, the remaining pseudowords will be practised in additional sessions after the 12th session until a total of 1200 productions is achieved.

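### Treatment may run past session 12, yet the probe meant to follow the last treatment session is fixed at session 12

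*Protocol*

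**What the plan says.** Section 6.6.1 defines treatment by the amount of practice. It states "The practise phase includes 100 attempts at producing the pseudowords", and where a session falls short, "the remaining pseudowords will be practised in additional sessions after the 12th session until a total of 1200 productions is achieved". It sets no limit on the number of additional sessions.

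The Procedures in section 6.2 define treatment by a session count. Item 4: "Treatment will be provided by a trained speech pathology student for one hour twice per week for six weeks". Item 6: "Immediately following the final (twelfth) session, participants will be asked to say the 70 word probe list and this will be recorded".

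Items 7 and 8 use a different anchor. Item 7 places the follow-up visits "one day, one week, two weeks and four weeks after finishing treatment", and item 8 reads "Four weeks after completion of the treatment, participants will also repeat several of the tasks completed in the initial assessment". Neither mentions session 12.

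Table 2 allots visits 9 to 22 to treatment and puts the one-day follow-up at visit 23. Section 6.14 plans within-participant contrasts across baseline, treatment and follow-up. It does not say to which phase the item 6 probe belongs.

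**The concern.** The two definitions of the end of treatment coincide only for a participant who completes every session in full. The protocol expects that some will not: section 6.6.1 has a rule for it, section 7.2 foresees fatigue and breaks, and section 8.1 allows a session to be discontinued.

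For such a participant, item 6 calls session 12 final when section 6.6.1 says more sessions are to come. Two things follow. The recording that reads as the close of treatment reflects an incomplete course, and nothing is scheduled immediately after the session that does close it. In addition, whoever analyses the data must decide whether the session 12 probe marks the end of treatment or is one more point within it.

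Few recordings fall in this stretch: before session 5, before session 9 and after session 12. With six participants, each analysed individually, one misplaced point is visible in that participant's series and one affected participant is a sixth of the study. Blinded scoring cannot correct the timing of a recording.

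**Working it through.** **Inputs.** Two sessions per week for six weeks (Procedures item 4); 100 productions per session and 1200 in total (section 6.6.1); treatment visits 9 to 22 (Table 2). The protocol gives no achieved production rates, so the rates below are assumptions shown over a range.

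**Step 1: the plan's own figure.** 2 x 6 = 12 sessions, and 12 x 100 = 1200 productions. The stated total reproduces exactly. It also shows that there is no slack: session 12 completes the 1200 only if all 100 are produced every time. With eleven full sessions and one of 90, the total is 11 x 100 + 90 = 1190, and section 6.6.1 already calls for an additional session.

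**Step 2: share delivered when the item 6 probe is taken.** At a constant r productions per session:

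- delivered by session 12 = 12r; share = 12r / 1200
- additional sessions = (1200 - 12r) / r, rounded up
- additional weeks = additional sessions / 2, assuming the twice-weekly pace continues

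| r per session | Delivered at session 12 | Share | Outstanding | Additional sessions | Additional weeks |
|---|---|---|---|---|---|
| 100 | 1200 | 100% | 0 | 0 | 0 |
| 90 | 1080 | 90% | 120 | 2 | 1 |
| 80 | 960 | 80% | 240 | 3 | 1.5 |
| 70 | 840 | 70% | 360 | 6 | 3 |
| 60 | 720 | 60% | 480 | 8 | 4 |

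**Step 3: does Table 2 settle it?** Visits 9 to 22 are 22 - 9 + 1 = 14 visits, against 12 sessions in the text, and the difference is not explained. If the two spare visits were meant for additional sessions, they would be enough only at 1200 / 14 = 85.7 productions per session, that is 86 or more. Table 2 therefore neither resolves the conflict nor covers the slower participants.

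**Step 4: which data are tied to session 12?** Only the item 6 probe. The probe list supplies the percentage of phonemes correct, a secondary outcome (section 6.5). The primary outcome is the intelligibility assessment. It is one of the initial assessment tasks (section 6.4.4), and if it is among those repeated, the repeat falls under item 8, which counts from completion of treatment.

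**Step 5: what do extended participants lack?** Under the literal schedule their last recording in the treatment period is the one at session 12, and the next is the one-day follow-up after the true last session. At 60 per session, 8 sessions and 480 productions would pass between the two without a probe.

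**The case against.** The strongest reply is that the text has a natural reading. Since 12 x 100 = 1200, the word in brackets in item 6 may give only the nominal number of the final session, with section 6.6.1 as the exception for incomplete sessions. The probe would then move with the last session. That is plausible, but the protocol does not say so, and staff following item 6 as written would record after session 12.

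A reader might go further and infer that the follow-up visits also fall inside treatment. If they were counted from session 12, then at 70 productions per session (3 additional weeks) the one-day, one-week and two-week visits would precede the end of treatment. Those visits hold 1 + 2 + 2 = 5 of the 6 follow-up readings of the list. At 60 per session the four-week visit would coincide with the end of treatment. The documents do not support this: items 7 and 8 count from the finish of treatment, and Table 2 places follow-up after the treatment block. Read literally, these visits move with the last session.

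Nor do the documents support a claim of distorted comparisons between participants. Sections 3.2 and 6.14 plan within-participant comparisons only.

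Three further points against the concern stand. A session 12 probe taken before additional sessions is still usable as a within-treatment point. The one-day visit captures the full delivered course a day later. Section 6.11 already provides for recording dosage at each session. These reduce the harm; they do not remove the contradiction between section 6.6.1 and Procedures items 4 and 6.

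**Conclusion.** The concern holds in a limited form. Section 6.6.1 and Procedures items 4 and 6 contradict each other for any participant who falls short of 100 productions in even one session. For that participant the item 6 probe precedes the end of treatment, and no probe is scheduled immediately after the last session.

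The exposure is one recording per affected participant, the secondary outcome derived from it, and the boundary between treatment and follow-up in the section 6.14 contrasts. The shares of 90%, 80% and 60% rest on assumed constant rates of 90, 80 and 60, and the additional weeks also assume that the twice-weekly pace continues. How many of the six participants would be affected cannot be known from the protocol. The primary outcome and the follow-up visits would be affected only if the finish of treatment were taken to mean session 12, a reading that the protocol does not require but should rule out. This is a minor-to-moderate correction.

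**What to change.** Reconcile Table 2, Procedures items 4 and 6, and section 6.6.1 on what counts as the end of treatment. How much treatment is given is for the investigators to settle. For data collection and analysis:

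- Tie the end-of-treatment probe in item 6 to the last treatment session actually delivered, including any additional sessions.
- State that the finish or completion of treatment in items 7 and 8 means that same session. The one-week satisfaction questionnaire in section 6.5 can use the same definition.
- If a probe is also kept at session 12 for participants with additional sessions, classify it as within treatment.
- Use the date of the last delivered session as the boundary between treatment and follow-up in section 6.14, and record that date with the dosage records already foreseen in section 6.11.
- Explain the 14 treatment visits in Table 2.

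The cost is a wording amendment, submitted as section 6.10 requires, and later visits for participants who need additional sessions. Those dates should be checked against the December 2025 close in section 6.8. The change needs to be made before the affected sessions take place, because a probe recorded at the wrong time cannot be retaken.
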